The SAPS will be performed at screening and four weeks later at baseline to identify subjects with persistence of sufficient delusional severity to enter the study. The clinical assessment battery will be comprised of the Psychotic Symptom Rating Scale (PSYRATS), Brief Psychiatric Rating Scale (BPRS), Scale for Assessment of Negative Symptoms (SANS), Calgary Depression Scale for Schizophrenia (CDSS), Clinical Global Impression (CGI) and Heinrich's Quality of Life Scale (QLS). We are using this broad battery of tests to compare treatment groups at baseline and to allow exploratory analyses to help us understand the effects of DCS on our primary outcomes and to guide selection of outcome measures for future studies. The clinical battery will be administered at baseline and weeks 4, 8, 12, 24, and, in most subjects,

Study #:S12-02991

36. In addition, the Delusion Subscale of the PSYRATS will be administered at weeks 2, 3, 6 & 10 to assess the time course of DCS effects on delusions. Ratings will be performed prior to the DCS/CBT session each week. Additionally, the Drug and Alcohol Questionnaire and the Pittsburgh Sleep Quality Index will be performed at baseline. Assessment of cognitive functioning will be measured by the MATRICS battery at baseline only since we have found no effect of daily or weekly DCS administration on this and similar cognitive batteries in four randomized controlled trials. The SAFTEE will be administered at weeks 3, 4, 8, and 12. The SAFTEE is a self-report measure on which the participant rates the severity of 55 side effects on a 4 point Likert Type scale. The scale also asks the participant to furnish an overall rating on the severity of all side effects. Participants will be followed regardless of whether they remain on study drug or comply with CBT sessions to permit an unbiased causal estimate of D-cycloserine treatment efficacy under the intention-to-treat principle. Additionally, a per protocol analysis will be performed using data only from subjects who have substantially complied with the protocol.

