Healthy subjects will be consented and screened for eligibility. Then, participants will perform a logical memory test, immediate recall test, and 25 minute recall. Participants will also perform a verbal fluency test. KVLT-R and BVMT-R and Rey Complex Figure test (RCFT).

Visit 2

Healthy subjects will perform the 1 week retrieval for the logical memory task, be given instructions for the scan test, and undergo the first set of MRI and fMRI scans.

Visit 3

Healthy subjects will complete the second set of MRI and fMRI scans.

Visit 4

Subjects will perform a memory recall task from the fMRI scan on visit 3 and a story segmentation task based on the fMRI scan on visit 2..

Data Analysis and Data Monitoring

Analysis Plan:

Primary: Between treatment differences in PSYRATS Delusions Subscale

Mean effects in week 12. The mean effect of DCS + CBT compared to Placebo + CBT on delusions will be tested using a linear mixed model repeated measures (MMRM) analysis of modified PSYRATS with fixed terms for study visit, DCS/Placebo treatment group and visit by treatment interaction. The model will include random subject effects. Baseline PSYRATS will be included in the model together with a baseline by treatment interaction term. The MMRM will assume a means model, an unstructured covariance matrix and parameter estimation will be based on restricted maximum likelihood. Because of the potential for failure of model convergence due to the requirement of a large number of interaction terms, only a few other covariates will be considered. These may include baseline SANS total score and demographic variables including age and gender, which may be predictive of outcome. To test treatment difference in change from baseline in PSYRATS, we will use a-pairwise contrast on the terms for DCS treatment by visit interaction. To examine differential treatment effects at each CBT week if there is significant interaction, we will perform tests of simple main effects. A significantly larger 12-week decline in mean PSYRATS total score for subjects receiving DSC supports the

Study #:S12-02991

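### The primary MMRM has no baseline-by-visit term, so the week-12 contrast may lose some precision; adding the term is a cheap improvement, not the correction of an error

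*Combined protocol and SAP*

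**What the plan says.** The Analysis Plan (Primary, mean effects in week 12) specifies a repeated-measures mixed model with "fixed terms for study visit, DCS/Placebo treatment group and visit by treatment interaction". On baseline it says: "Baseline PSYRATS will be included in the model together with a baseline by treatment interaction term". On covariance and estimation: "The MMRM will assume a means model, an unstructured covariance matrix and parameter estimation will be based on restricted maximum likelihood". The treatment comparison is described as follows: "we will use a-pairwise contrast on the terms for DCS treatment by visit interaction". The plan limits further adjustment on convergence grounds: "Because of the potential for failure of model convergence due to the requirement of a large number of interaction terms, only a few other covariates". A baseline-by-visit term is not listed there or anywhere else, and a constant baseline slope is neither mentioned nor justified.

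The Assessments section sets the rating times. For the full battery: "The clinical battery will be administered at baseline and weeks 4, 8, 12, 24, and, in most subjects"; the last time point listed is week 36. For the delusions subscale alone: "the Delusion Subscale of the PSYRATS will be administered at weeks 2, 3, 6 & 10". On timing within a visit: "Ratings will be performed prior to the DCS/CBT session each week". The on-treatment ratings available are therefore weeks 2, 3, 4, 6, 8, 10 and 12. The model description refers only to study visit and does not say which of these enter the primary model.

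**The concern.** With baseline and baseline-by-treatment but no baseline-by-visit, the slope on baseline may differ between arms but not between visits. Under an unstructured covariance, generalised least squares gives most weight to the visits where baseline predicts best. If prediction weakens with time, those are the early ones.

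The schedule makes that pattern plausible. Under CBT/DCS Protocol, both arms receive placebo before sessions 1 and 2, and randomised drug starts at session 3. If session number equals week number, the week-2 and week-3 ratings precede any randomised drug and come close to retests of baseline. Week 12 comes after most of the treated sessions.

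At stake is some precision in the one comparison that decides a trial of 60 evaluable subjects, when the data needed to avoid the loss are already being collected.

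**Working it through.** **The plan's own figure.** Estimation of statistical power gives 60 evaluable subjects, 1:1 allocation (30 per arm) and an effect of 0.8 SD; the Analysis Plan gives two-sided 0.05. The standard error is √(2/30) = 0.258 SD and 0.8/0.258 = 3.10, so power is Φ(3.10 − 1.96) = 87.3%. The noncentral t with 58 df gives 86.1%. Both agree with the stated power above 85%. That calculation uses no baseline adjustment.

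**Assumptions for the check (none of these values is in the documents).** Every rating has SD 1 and data are complete. Ratings at weeks 2, 3, 4, 6, 8, 10 and 12 are modelled, and follow-up ratings are left out. The correlation between ratings at times s and t is k·ρ^|s−t|, where k is reliability (1.0, 0.9 or 0.8) and k·ρ^12 = r is the baseline-to-week-12 correlation (0.3, 0.5 or 0.7).

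**Formulas.** Let β be the vector of visit-specific baseline slopes and R the residual covariance given baseline.
- Common slope: b = (1′R⁻¹β)/(1′R⁻¹1).
- Week-12 variance with visit-specific slopes: V = 1 − r².
- Week-12 variance with a common slope: V = 1 − r² + (b − r)².
- Power at 0.8 SD: Φ(0.8/√(2V/30) − 1.96).

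**Worked case, r = 0.5, k = 1.0.** The visit slopes fall from 0.89 at week 2 to 0.50 at week 12. Week 2 alone carries 85% of the weight, and b = 0.841. The variances are 0.750 with visit-specific slopes and 0.750 + 0.341² = 0.866 with the common slope, a ratio of 1.155. Since 60/1.155 = 51.9, this is like losing about 8 of 60 subjects. Power is 94.7% with the term and 91.5% without.

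**Range.**

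| r | k | common slope b | weight on weeks 2–4 | variance ratio | power, as planned | power, with term |
|---|---|---|---|---|---|---|
| 0.3 | 1.0 | 0.70 | 76% | 1.178 | 84.9% | 90.1% |
| 0.3 | 0.9 | 0.62 | 71% | 1.109 | 86.9% | 90.1% |
| 0.3 | 0.8 | 0.55 | 65% | 1.068 | 88.2% | 90.1% |
| 0.5 | 1.0 | 0.84 | 86% | 1.155 | 91.5% | 94.7% |
| 0.5 | 0.9 | 0.74 | 78% | 1.079 | 93.1% | 94.7% |
| 0.5 | 0.8 | 0.67 | 69% | 1.038 | 94.0% | 94.7% |
| 0.7 | 1.0 | 0.93 | 93% | 1.101 | 98.5% | 99.1% |
| 0.7 | 0.9 | 0.83 | 78% | 1.032 | 99.0% | 99.1% |
| 0.7 | 0.8 | 0.76 | 61% | 1.006 | 99.1% | 99.1% |

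In the first row the adjusted variance is 0.91 + 0.402² = 1.07, which is 7% above no adjustment at all (power 87.3%).

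**Where the loss shrinks.** With only weeks 4, 8 and 12 in the model, the ratio is at most 1.07 over the same grid. If the SD grows 1.4-fold by week 12 (k = 0.9), the standard error rises by 0.1% to 2.7%. With constant correlations and constant SD the ratio is exactly 1.

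**Check at the trial's size.** Simulation with 60 subjects, 600 runs per pattern, an REML-type unstructured fit and baseline-by-treatment in both models gave these variance ratios:
- r = 0.5: 1.12, 1.07 and 1.04 for k = 1.0, 0.9 and 0.8.
- k = 0.9: 1.13 at r = 0.3 and 1.04 at r = 0.7.
- Constant correlation: 0.98, so the extra term cost about 2%.

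With no true effect, mean estimates stayed within 0.012 SD of zero. Type I error was 0.042–0.067 with the common slope and 0.045–0.060 with the added term; the Monte Carlo standard error is √(0.05·0.95/600) = 0.009.

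**The case against.** The case for leaving the model alone has real force. The documents give no correlations, so the loss is conditional. The upper end needs ratings without measurement error, yet Rater Training asks raters to hold only a correlation of 0.8 with gold-standard ratings. That is not test-retest reliability, but it makes an error-free pattern a weak anchor. The visit set is not stated either: the extra subscale ratings are described as serving the time course, and a model on weeks 4, 8 and 12 loses less. At the design effect of 0.8 SD most scenarios lose 0 to 3 points. All of this stands and limits the size of the point. The convergence remark does not settle the matter, because it concerns other covariates. Six mean parameters are few beside the 7 × 8/2 = 28 covariance parameters that seven visits already require.

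Some stronger readings are tempting but unsupported:
- **The week-12 estimate is biased or the test invalid.** With complete data neither is so; the simulations show neither.
- **A chance baseline imbalance is a second harm.** The shift averages to zero under randomisation and is the same variance already counted.
- **The power claim is wrong.** It assumes no baseline adjustment and reproduces.
- **The missing-at-random statement fails.** A misfitting slope could matter under dropout, but the week-12 difference separated from that of the fuller model only when dropout was made to depend on the last score in opposite directions by arm. It did not with the same mechanism in both arms, and nothing in the documents points to opposing mechanisms.

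**Conclusion.** The point holds as a modest, conditional efficiency gain. The plan holds the baseline slope constant over visits within each arm and gives no reason for it. If correlation with baseline declines, week-12 variance is about 1% to 18% larger than it need be (4% to 16% at r = 0.5). Power at 0.8 SD is then 0 to 5 points lower, for example 91.5% to 94.0% against 94.7% at r = 0.5. Power stays above 85% in every scenario tried except the most extreme, at 84.9%. These figures rest on assumed correlations, complete data and all seven on-treatment ratings being modelled. Because the term costs little when it is not needed, adding it is sensible; leaving it out would not invalidate the analysis.

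**What to change.** Add a baseline-by-visit interaction to the primary MMRM. Keep the planned baseline-by-treatment term, centre baseline at its overall mean so that the treatment-by-visit contrast refers to a subject with average baseline, and take the week-12 treatment difference from that model. State which visits enter it. Make the change before unblinding.

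Cost: one more term in the model statement, about six extra fixed-effect parameters with seven visits, no new data, and roughly 2% in variance if the slope turns out to be constant. Entering baseline as a further response with equal arm means is not an interchangeable alternative here, because under one common covariance it would drop the planned baseline-by-treatment term.

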Study recruitment, enrollment, and retention will be monitored to insure that recruitment goals are attained. Study screening information is reviewed by comparing the characteristics of subjects enrolled versus screened out, assisting with potential strategies to improve study enrollment. The ratio of screened to randomized subjects is also reviewed to reflect the effort required to successfully enroll subjects in the study. Research study visit attendance will also be monitored on an ongoing basis.

Estimation of statistical power: We will enroll up to 100 subjects until 60 are evaluable, defined as completing the week 3 clinical assessment which is the first clinical assessment following study drug administration. Subjects will be randomly assigned to DCS or Placebo in a 1:1 ratio. This sample size provides greater than 85% power to detect an effect size of 0.8 in the two-group mean comparisons of 12-week PSYRATS Delusions Subscale total score, which we consider to be clinically-significant. We found an effect size of 0.8 for the difference between treatment groups in our two-session pilot trial and expect a substantially larger effect with 10 DCS-facilitated CBT sessions in this trial. Further, the sample size provides greater than 95%

Study #:S12-02991

power to detect a difference in the response rate of DCS vs placebo assuming the response rate for placebo is 10% and the response rate for DCS is 50%.

Risk/Benefit Assessment

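### The primary test names no visit: it should be defined as the week-12 difference in adjusted means, and the random subject effect dropped if the unstructured matrix is the residual one

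*Combined protocol and SAP*

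**What the plan says.** All of this is in the combined protocol and SAP, mainly under Analysis Plan, Primary.

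- **Target.** The paragraph is headed "Mean effects in week 12", and the result that counts as success is "A significantly larger 12-week decline in mean PSYRATS total score" on DCS.
- **Model.** Fixed terms are visit, treatment and their interaction. "Baseline PSYRATS will be included in the model together with a baseline by treatment interaction term".
- **Test.** "To test treatment difference in change from baseline in PSYRATS, we will use a-pairwise contrast on the terms for DCS treatment by visit interaction". The visits and coefficients are not named. A separate sentence gives week-by-week treatment effects by simple main effects, if the interaction is significant.
- **Covariance.** "The model will include random subject effects". "The MMRM will assume a means model, an unstructured covariance matrix", with REML. Other covariates are kept few: "Because of the potential for failure of model convergence due to the requirement of a large number of interaction terms". No fallback structure is named.
- **Power.** Estimation of statistical power refers to "two-group mean comparisons of 12-week PSYRATS Delusions Subscale total score": 60 evaluable subjects, 1:1, effect size 0.8, power above 85%.
- **Ratings.** Under Assessments, the subscale is rated at baseline and weeks 2, 3, 4, 6, 8, 10 and 12, then at week 24 and, for most subjects, week 36. The analysis plan does not say which ratings enter the model.
- **Therapist.** CBT/DCS Protocol allows a second therapist and balances the arms within therapist. The analysis model has no therapist term.

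**The concern.** With baseline as a covariate, the visit levels on the ordinary reading are the post-baseline weeks only. A pairwise contrast between two treatment-by-visit terms is then the change in treatment effect from one post-baseline week to another. It is neither the week-12 difference nor a difference in change from baseline.

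The slip is easy to make. If software takes week 2 as the reference visit, the single coefficient labelled treatment by week 12 is exactly the week-12-minus-week-2 contrast. The week-12 difference needs the treatment main effect added to it. Because treatment also interacts with baseline, it needs a stated baseline value as well.

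At stake are which effect the primary test addresses and how much power it has. The tertiary mediator analyses reuse the same model, so its wording carries over to them. The covariance wording is a second, smaller matter: it may ask the software to estimate a variance that the data cannot separate from the rest.

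**Working it through.** **Inputs.** From Estimation of statistical power: d = 0.8, 60 evaluable, 1:1, so n = 30 per arm. From the Analysis Plan: two-sided 0.05. Seven ratings to week 12, from Assessments. Assumed, not in the documents: between-visit correlation ρ = 0.5 (range 0.4 to 0.7), SD 1 at every visit, complete data.

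**1. The plan's own figure.** Unadjusted two-sample t-test at week 12: SE = √(2/30) = 0.258; noncentrality 0.8/0.258 = 3.10; 58 df; power 86.1%. The stated figure of above 85% is reproduced.

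**2. What each contrast estimates.** Write the mean as μⱼ + τT + γⱼT + β(B − B̄) + δT(B − B̄), where j is the visit, T the arm and B baseline.
- Week-12 difference at mean baseline: τ + γ₁₂.
- Pairwise contrast of interaction terms: γ₁₂ − γₖ = (τ + γ₁₂) − (τ + γₖ). The main effect τ cancels. The baseline terms are common to all visits and cancel too, so baseline adjustment gives no gain in precision.

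**3. Standard errors.**
- Week-12 difference: √[(2/30)(1 − ρ²)] = √(0.0667 × 0.75) = 0.224.
- Week 12 minus week k: √[(2/30) × 2(1 − ρ)] = √(0.0667 × 1) = 0.258.

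**4. Power (noncentral t, 57 df).** Let f be the share of the week-12 effect already present at the earlier visit.

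| Contrast | ρ = 0.4 | ρ = 0.5 | ρ = 0.7 |
|---|---|---|---|
| Week-12 difference | 91% | 94% | 99% |
| Week 12 minus earlier, f = 0 | 79% | 86% | 98% |
| Week 12 minus earlier, f = 0.25 | 55% | 63% | 84% |
| Week 12 minus earlier, f = 0.5 | 28% | 33% | 50% |

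At ρ = 0.5 the unadjusted week-12 test (86.1%), the adjusted one (94.0%) and week 12 minus an effect-free visit (86.1%) all exceed 85%. The power statement therefore does not settle which was meant.

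**5. Simulation with an estimated unstructured matrix** (2,000 trials per setting). With exchangeable correlation 0.5, power was 93% to 95% for week 12 and 84% to 86% for week 12 minus week 2. With correlation decaying over time (0.5 at a six-week gap), it was 81% to 83% and 72% to 73%. Rejection under the null was 3.8% to 5.4%.

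**6. Covariance.** Seven ratings give 7 × 8/2 = 28 unstructured parameters. A random-intercept variance makes 29. It adds the same constant to every element of the matrix, which the 28 parameters can already reproduce, so the rank stays 28. With weeks 24 and 36 included, the count is 9 × 10/2 + 1 = 46, with rank 45. The marginal covariance, and hence the treatment estimate, is unaffected.

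**7. Therapist.** If a factor balanced across arms explains a share s of residual variance and is left out, the t statistic shrinks by √(1 − s). The true size is P(|t₅₇| > 2.002/√(1 − s)). For an assumed s = 0.05 the cut-off is 2.054 and the size 4.45%; for s = 0.15 it is 2.172 and 3.4%. If 5% to 15% is instead a share of total variance, divide s by 0.75 (ρ = 0.5): 4.3% to 2.9%.

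**The case against.** The strongest reply is that the intent is plain. The heading, the success sentence and the power section all point to week 12. The test sentence itself says its target is change from baseline, which no contrast of two post-baseline visits can be. The plan also says it assumes a means model. On a cell-means reading, a pairwise contrast is naturally DCS against placebo within a visit, and with baseline as a covariate the week-12 adjusted difference is the adjusted difference in change. A change-score response would lead to the same test.

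This stands, and it makes the week-12 reading the likely one. It does not supply the visit, the coefficients or the baseline value.

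Several stronger readings are tempting, but the documents do not support them:

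- **That power collapses.** A reader might note that the rationale for the protocol design expects a plateau between weeks 4 and 8, so that week 12 minus a late visit could be near zero. No section names a late comparison visit. Those weeks belong to an earlier eight-week study of weekly dosing; here randomised dosing starts at session 3, so the fourth to eighth doses fall at sessions 6 to 10. The 63% and 33% figures likewise need an earlier visit that nobody has proposed.
- **That the week-12 test depends on a significant interaction.** That condition is attached to the week-by-week tests.
- **That type I error or the estimate is compromised.** Each contrast alone keeps about 5%, and the redundant variance does not bias the effect.
- **That the random effect is certainly redundant.** This holds if unstructured describes the residual matrix, the usual MMRM meaning, which the plan does not state. The plan attributes its fear of non-convergence to interaction terms, not to this.
- **That the week-3 rating is plainly contradictory.** CBT/DCS Protocol gives study drug one hour before the session, and Assessments puts ratings before the DCS/CBT session. Estimation of statistical power calls week 3 the first clinical assessment after study drug. Assessment of memory consolidation places a test within that pre-session hour, and a rating there would fit all of these. The order is unclear, not clearly inconsistent.

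**Conclusion.** The point holds as a gap in specification that should be fixed, not as a certain error. The primary test sentence does not define the week-12 comparison that the rest of the plan aims at, and its literal form is a different contrast.

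If it were implemented as week 12 minus a visit with no effect yet, power would fall from about 94% to about 86% at correlation 0.5, and from 91% to 79% at 0.4 or 99% to 98% at 0.7. This rests on 30 per arm, d = 0.8, equal SDs and complete data; the simulation with an estimated matrix gives a loss of about 8 to 11 points. Larger losses need an earlier visit that already carries part of the effect.

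The random subject effect is redundant if the unstructured matrix is the residual one. The consequence is a risk of non-convergence. Leaving out therapist, if more than one treats, makes the test slightly conservative (size about 3% to 4.5% under the assumed shares). The timing of the week-3 rating is a separate ambiguity that does not alter a correctly defined week-12 test.

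**What to change.** In the primary analysis section:

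1. Define the primary test as the DCS-minus-placebo difference in adjusted means at week 12 (treatment term plus its week-12 interaction term), evaluated at the overall mean baseline with baseline centred.
2. State that it is tested whatever the interaction result.
3. State that baseline is a covariate only, and list the ratings that enter the model, including whether weeks 24 and 36 do.
4. Drop the random subject effect, say that the unstructured matrix is the residual covariance, and name a fallback order in advance, for example heterogeneous Toeplitz, then compound symmetry.
5. Add therapist as a fixed effect if more than one treats, since the arms are balanced within therapist.

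Separately, reconcile CBT/DCS Protocol, Assessments, Assessment of memory consolidation and Estimation of statistical power on whether the week-3 rating comes before or after the first randomised dose.

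The cost is wording, plus one or two degrees of freedom if therapist is added. Visits, data collection and sample size do not change.

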conference and will monitor treatment fidelity by evaluating audiotapes from 20% of sessions using the Cognitive Therapy for Psychosis Adherence Scale (CTPAS) (34). [name] recently participated in the development of the CBT protocol and conducted trainings for the NIMH-funded RAISE Study. Competency will be defined as a score of at least 10 on the CTPAS. Competency must be achieved by each study therapist with a pilot case prior to participation in the study and must be maintained throughout the study. Additional training will be provided if CTPAS scores drop below 10.

Rationale for DCS/CBT protocol design: The design of our protocol for combining DCS with CBT follows from several findings: 1.) DCS effects may decrease over time with repeated dosing (21) although we believe that once-weekly dosing reduces the risk of tachyphylaxis, 2.) DCS is effective for novel learning only (22) and 3.) we previously found large effects when DCS was combined with the first of two sessions of an alternative beliefs exercise which was designed to exploit DCS effects on memory consolidation and cognitive flexibility (32). Therefore, we will begin with two introductory sessions unaccompanied by study drug; study drug will first be administered with an alternative beliefs exercise at session #3. We will then continue weekly study drug administration one hour prior to CBT sessions and will follow session #3 with a second session of the alternative beliefs exercise in order to replicate the intervention provided in our pilot trial (two consecutive sessions of an alternative beliefs exercise) since delusions continued to improve following the second exposure to the exercise. The remaining 8 sessions will consist of standard CBT approaches to delusions to consolidate therapeutic effects.

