effectiveness of DCS. The probability of a type one error, the size of the test, will be controlled at 0.05, and all tests will be two-tailed. Overall alpha will be maintained at 0.05 for analyses of primary parameters. No adjustments will be made for multiplicity among secondary parameters analyzed. *Missing data*: The analysis will utilize the intention-to-treat principle. All randomized subjects, both completers and non-completers, will be included in the analysis without imputation. Estimates will be unbiased if follow-up data that are missing are "missing at random" conditional on the observed data and model assumptions.

Secondary: Characterizing onset and duration of effectiveness of DCS

a and b. Testing equality of the distributions of onset and duration. Onset is defined as the first week at which the criterion for response is met that lasts at least to the final week of the treatment period. Kaplan-Meier estimates of the survival distributions of time to onset of response will be obtained and the survival distributions will be compared using the log-rank test. The survival distribution, $H(t)$, is the probability that onset will occur after time t . Duration is defined as the number of weeks from onset to offset. Offset for a responder is the first week at which the criterion for response is no longer met. The treatment specific survival distributions of duration will similarly be compared using the log-rank test. The null hypothesis for the second primary outcome measure is that there is no difference between the two treatment groups in the proportion of subjects who are responders (defined as a 20% or greater reduction in PSYRATS Delusions Subscale total score) beginning in week two to the end of the treatment phase. The statistical analysis will be based on a repeated measures logistic regression model. The independent terms in the model will include the same variables and covariates used in the MMRM analysis. By the definition of responder, there cannot be any missing data.

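### Duration of response is counted from onset, so its log-rank test mixes speed of onset with persistence, and hypothesis 2b has no test of its own

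*Combined protocol and SAP*

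**What the plan says.** The definitions are in the Analysis Plan, under the Secondary heading on onset and duration, items a and b.

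- Onset: "Onset is defined as the first week at which the criterion for response is met that lasts at least to the final week" of treatment.
- Offset: "Offset for a responder is the first week at which the criterion for response is no longer met".
- Duration: "Duration is defined as the number of weeks from onset to offset".
- Test: "The treatment specific survival distributions of duration will similarly be compared using the log-rank test".
- Response: "defined as a 20% or greater reduction in PSYRATS Delusions Subscale total score".

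The Assessments section fixes when response can be observed: "The clinical battery will be administered at baseline and weeks 4, 8, 12, 24, and, in most subjects", with week 36 ending the sentence. The delusions subscale is also rated at weeks 2, 3, 6 and 10. After week 12 there are thus at most two ratings.

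Under Specific Aims and Design, hypothesis 2a expects the DCS response rate to be ahead early, after two weeks of drug. Hypothesis 2b defines persistence by state at fixed times: still at least 20% below baseline at the 3 and 6 month follow-ups. That definition does not involve the onset date.

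No other planned analysis reaches those visits. The primary MMRM contrast is at week 12, the repeated-measures logistic model stops at the end of treatment, and the cure model concerns onset.

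**The concern.** Because an onset must survive to week 12, no counted responder can have an offset by week 12. The interval from onset to week 12 enters duration automatically, and it is longer for earlier responders. Two arms that lose response at the same rate after treatment will differ in duration if they differ in onset, and hypothesis 2a predicts such a difference in favour of DCS. A significant duration result could then be reported as evidence for 2b when it only restates 2a.

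A second, smaller consequence concerns loss during treatment. A subject who responds at weeks 4 to 10 and has lost response by week 12 has no onset and does not enter the duration analysis. The protocol raises the possibility itself, in the rationale for the DCS/CBT design: "DCS effects may decrease over time with repeated dosing". The two analyses meant to describe time course code that subject as never having had an onset.

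**Working it through.** **1. The plan's own figures.** The documents give none for the duration test. The section on statistical power gives 60 evaluable subjects (30 per arm), two-sided 0.05. Its figure of more than 85% for an effect size of 0.8 reproduces (86.1%, t test). Its figure of more than 95% for 10% vs 50% response comes out at 94.9% (exact chi-square power), marginally short, and nothing here depends on it. The same rates give expected responders of 30 x 0.50 = 15 on DCS and 30 x 0.10 = 3 on placebo.

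**2. Decomposition.** For any counted responder,

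duration = offset - onset = (12 - onset) + (offset - 12).

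The first term depends on onset alone. The second is persistence after treatment. It can be observed only as 24 - 12 = 12 or 36 - 12 = 24 weeks, or is censored.

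**3. Hand example.** Three subjects are all found to have lost response at week 24:

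| Onset week | Credited before week 12 | After week 12 | Duration |
|---|---|---|---|
| 4 | 8 | 12 | 20 |
| 10 | 2 | 12 | 14 |
| 12 | 0 | 12 | 12 |

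Persistence is identical. The 8-week spread is all onset.

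**4. Simulation with identical loss.** There were 4,000 trials per scenario. Onsets fell on the scheduled ratings. The probability of loss at each follow-up visit was the same in both arms (30% or 50% at week 24, and the same again at week 36 among those remaining). Everyone was rated at week 36 and those still in response were censored there. Responder numbers were 15 vs 3, 15 vs 8, 15 vs 15, 20 vs 10, or drawn at the plan's 50% and 10% of 30. The onset distributions and loss rates are assumptions, since the documents give neither.

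| Mean onset week, DCS vs placebo | Rejection, duration from onset | With responders drawn at 50% and 10% | Rejection, time from week 12 |
|---|---|---|---|
| 7.5 vs 7.5 | 5.0-7.7% | 6.8-7.6% | 3.6-5.7% |
| 6.2 vs 8.55 | 8.9-14.7% | 12.2-14.7% | 3.6-5.7% |
| 4.5 vs 10.0 | 19.4-39.6% | 20.2-30.2% | 3.6-5.7% |

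In the two shifted rows nearly all rejections favour DCS. For example, at 15 vs 3 with the large shift and 50% loss, 26.6 of the 26.8 percentage points do.

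**5. Sensitivity.** The large shift puts 30% of DCS onsets at week 3, the week of the first active dose, so it is best read as an outer case. With onsets restricted to weeks 4 to 12 and 50% loss (3,000 trials per scenario), mean onsets of 6.8 vs 9.2 weeks give 12.8-14.6% and 5.7 vs 10.3 weeks give 23.5-29.2%, against 4.3-5.8% counted from week 12. A smaller shift, 6.8 vs 8.0 weeks, gives about 10% at 15 vs 3 and 7% at 15 vs 15.

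**The case against.** Duration from onset is a legitimate quantity. If DCS responders respond sooner and lose response at the same visits, they have spent longer in response, and the log-rank test correctly detects that. A reader might take the rejection rates above as type I error of the test as written. They are not, because its null is equality of duration from onset, and that null is false when onset differs. This part of the objection stands. The complaint is that the quantity does not match hypothesis 2b.

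A reader might also infer that loss before week 12 is invisible throughout the plan. The documents do not support that. The MMRM uses every on-treatment rating, has a visit-by-treatment term, and provides for tests at individual weeks if the interaction is significant. An early effect that faded could show there, and possibly in the repeated-measures logistic model. Nor do the documents treat fading as likely: the same rationale expects once-weekly dosing to lessen it, and the sponsor's eight-week cognitive remediation study reports no loss of efficacy.

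Requiring a sustained onset is a deliberate and defensible choice, since time to first response would count transient dips. The sizes rest on assumed inputs, and at 15 vs 3 the test rejects in about 6-8% of trials even with equal onset. Finally, this is one unadjusted secondary analysis in a proof-of-concept trial, and the Kaplan-Meier onset curves would show any onset difference beside it.

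**Conclusion.** The mechanism follows from the definitions and is not in doubt: earlier onset lengthens duration when loss of response is identical, and the plan has no separate test of hypothesis 2b. The direction favours DCS if onset is earlier on DCS, as 2a expects; earlier placebo onset would reverse it. The size is illustrative. Under the assumed onset and loss rates, rejection is roughly 9-15% for a moderate shift and 19-40% for a large one, against about 4-6% when counted from week 12. With small shifts or equal onset it is close to nominal, apart from small-sample behaviour.

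The primary analysis is unaffected. The point should be corrected because a named secondary hypothesis otherwise rests on a measure that cannot separate it from another one.

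**What to change.** In the Secondary part of the Analysis Plan, items a and b:

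1. Test 2b by comparing, in all randomised subjects, the proportion at least 20% below baseline at week 24 and at week 36. Because only most subjects are rated at week 36, state how those without a rating are handled.
2. As support, in subjects responding at week 12, count time to loss from week 12 with a discrete-time comparison, since loss is known only to a 12-week interval. State that this is a post-randomisation subset, about 15 vs 3 under the plan's rates, so it is not a randomised comparison and has little power.
3. Keep the onset analysis separate. If duration from onset is retained, label it total time in response and do not interpret it as persistence.
4. Tabulate by arm the subjects who met the response criterion and lost it before week 12.

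The cost is SAP wording and small extra analyses on ratings already scheduled. The downside is that the persistence measure no longer credits on-treatment weeks, which the onset analysis already covers.
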